6.0 STATISTICAL AND ETHICAL CONSIDERATIONS

Subject Accrual

Subjects of both genders, from all racial and ethnic groups are eligible for this trial if they meet the criteria outlined in Section 4. To date, there is no information that suggests differences in drug metabolism or disease response among racial or ethnic groups or between the genders, indicating that results of the trial will be applicable to all groups. Most tibial pseudarthrosis arises in early childhood, with fewer cases after age 11; thus we anticipate an enrollment of younger children. If differences in outcome that correlate to gender, age, racial, or ethnic identity are noted, accrual may be expanded or additional studies may be performed to investigate those differences.

6.1 Statistics and Feasibility

The primary objective of this study is to determine if there is improved healing of tibia in patients treated with BMP-2, compared to those treated with standard surgical protocol alone. The primary outcome for the study will be radiographic evidence of tibial healing 12 months after surgery, using the RUST criteria as described in section 6.4. For each cortex a score of 1, 2, or 3 will be given. A non-visible cortex will be given a score of 1. The cortex scores will be added together for a total score. We will define three levels of healing: RUST score of 4-7, score 8-9, or score 10-12. The primary analysis will be to compare the distribution of scores across the 3 groups (4-7, 8-9, 10-12) at 12 months post-surgery using a Wilcoxon Test. The proportion of patients achieving **complete healing** (score 9-12, with at least 2 evaluable cortices having a score of 3) will also be calculated and an exact 95% confidence interval computed.

Analyses based on the actual 4 – 12 scores will also be performed and compared between the two groups. In addition, the % of patients having a **successful outcome** (defined as RUST score of 9 or greater, with at least 2 evaluable cortices having a score of 3) will be compared between the two groups. Time to union will be compared between the two groups based on Xrays obtained at 5 points after surgery (6 weeks, 3 mos, 6, 9, and 12 mos).

Subjects who experience a serious treatment-related adverse event, refracture, or need for reoperation will be considered to be **study failures**. The proportion of failures within each group will be compared to assess safety success.

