4.0 METHODOLOGY

4.1 Overview of Proposed Study

This phase II, single-blind, randomized study will evaluate children with neurofibromatosis type 1 (NF1) who undergo surgical management of tibial pseudarthrosis. The rationale is predicated on the observation that union of tibial fracture in patients with NF1 is difficult to achieve without extraordinary measures to optimize bone healing, and that deficits in bone formation as well as excessive bone resorption occur in NF1. The preliminary success in improved rate of tibial fracture healing when rhBMP-2 is locally applied intra-operatively, as outlined by [name] et al. (2010), has influenced the need for a carefully controlled clinical trial to document efficacy and safety of this device. Outcomes of this trial will likely influence surgical decisions in management of patients with NF1 and TPA.

Children with NF1 and TPA whose primary orthopedic surgeon deems surgical intervention is required are eligible for this trial. At time of enrollment, participants will be offered participation in a preference arm or randomized arm, and will be assigned to the BMP-2 or control group based on these choices. Surgery must take place at one of the participating consortium sites, and the standard surgical approach will include: extensive resection of abnormal pseudarthrotic

material, tibial osteotomy, placement of an intramedullary rod, and autogenous bone graft from the iliac crest to the osteotomy tibial gap. Those in the BMP-2 group will in addition have INFUSE in a collagen sponge wrapped around the tibia during the surgical process.

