Unanticipated Adverse Device Effects: An unanticipated adverse device effect is any serious adverse effect on health or safety, any life-threatening problem or death caused by, or associated with a device, if that effect, problem or death was not previously identified in nature, severity or degree of incidence in the IDE application. Or, any other unanticipated serious problem associated with a device that relates to the rights, safety or welfare of participants.

Common Terminology Criteria for Adverse Events (CTCAE)

This study will utilize the CTCAE of the National Cancer Institute for reporting of adverse events. A copy of the current version of the CTCAE version 4.03 can be downloaded from the CTEP home page: <http://ctep.cancer.gov/reporting/ctc.html>

Attribution: Definitions of relationship to study medical device are as follows:

Unrelated: bears no relation to timing of medical device use, similar to symptoms or signs expected in the disease process, does not recur on rechallenge.

Unlikely: does not have temporal relationship to intervention, could readily have been produced by the subject's clinical state, environmental, or other interventions, does not reappear or worsen with reintroduction of intervention.

Possibly: bears relation to timing of medical device use, similar to symptoms or signs expected in the disease process, does not recur on rechallenge.

Probably: bears clear relation to timing of medical device use, distinct from symptoms or signs expected in the disease process, does not recur on rechallenge.

Definitely: bears clear relation to timing of medical device use, distinct from symptoms or signs expected in the disease process, occurs on rechallenge.

The expected adverse events related to administration of BMP-2 are listed in **Section 2.1 and in the Informed Consent Forms**. All other adverse events not attributed to BMP-2 will be considered unexpected. Adverse events attributable to BMP-2 will also be reported if the adverse events are at an intensity that is more severe than previously documented or considered significant by the investigator and noted in the product insert and/or protocol.

Reporting Procedures for All Adverse Events

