All observed or volunteered adverse events, regardless of suspected causal relationship to study medical device will be recorded as Adverse Events in the electronic data system at the time of surgery and at each follow-up visit, and entered into the electric system within 2 weeks of the visit. Events involving adverse reactions to the device, illnesses with onset during the study, or exacerbation of pre-existing illnesses should be recorded. Objective test findings (e.g., abnormal laboratory test results) should also be recorded.

As the investigational intervention (INFUSE bone graft) occurs only at the time of surgery, it is not expected that adverse events noted at follow-up visits would require removal of a participant from the study. If a subject voluntarily withdraws from the study, he or she will be given appropriate care under medical supervision until symptoms cease or until the condition becomes stable.

The severity of toxicities will be graded in accordance with the Common Terminology Criteria for Adverse Event (CTCAE) version 4.03 (<http://ctep.info.nih.gov>).

The relationship of adverse events to the medical device will be assessed by the physician using the categories of “unrelated, unlikely, possibly, probably, or definitely” as listed above.

Expedited Reporting Guidelines

The following adverse events require expedited reporting as required by 21CFR812.150:

- All adverse events that are both serious and unexpected per section 2.1.
- Adverse events that might influence the benefit-risk assessment of administration of INFUSE as outlined in the protocol
- All grade 5 adverse events
- A serious adverse event that occurs within 30 days of the placement of an investigational device
- Expedited AE reporting timelines defined:

“24 hours; 3 calendar days” – The investigator must initially report the AE within 24 hours of learning of the event to Operations Center followed by a complete report within 7 calendar days of the initial 24-hour report. All adverse events must be entered into the electronic data system.

Adverse events requiring expedited reporting will be reported and documented on a designated Serious Adverse Event case report form developed for this protocol, “NF Clinical Trials Consortium Operations Center IDE Serious Adverse Event Form for IDE# G140004” and forwarded to:

NF Clinical Trials Consortium Operations Center
Research Nurse Manager: [name] BSN
Regulatory Compliance: [name]
Phone: [name]: [contact] / [name]: [contact].

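### The safety composite in 6.1 counts serious events only if treatment-related, a term left undefined, and the only attribution scale refers to a device that controls do not receive, so this component is not counted alike in both groups

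*Combined protocol and SAP*

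**What the plan says.** Section 6.1 defines the composite: "Subjects who experience a serious treatment-related adverse event, refracture, or need for reoperation will be considered to be" study failures. Its use follows directly: "The proportion of failures within each group will be compared to assess safety success". No test, significance level or power is attached, and treatment-related is not defined there.

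Section 5.9 contains the protocol's only graded attribution scale: "Attribution: Definitions of relationship to study medical device are as follows". The rater and the object are stated once more under the reporting procedures: "The relationship of adverse events to the medical device will be assessed by the physician". The third of the five grades reads: "Possibly: bears relation to timing of medical device use, similar to symptoms or signs expected in the disease process, does not recur on rechallenge". It differs from the *Unrelated* grade only in the timing element.

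Exposure differs by group. Section 4.1 says of the surgical procedure: "Those in the BMP-2 group will in addition have INFUSE in a collagen sponge wrapped around the tibia during the surgical process". Controls have the same operation without the device.

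Under Blinding in 4.2.3, subjects, parents and surgeons in the Choice Arm know the treatment. In the Randomized arm the surgeon and one coordinator or operating-room technician know it, while a site PI who is not the surgeon is blinded.

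Section 5.9 also has all adverse events recorded whatever their suspected cause.

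**The concern.** A between-group safety comparison needs an event definition that a child in either group can meet on the same terms. Here the serious-event component depends on relatedness, and the only written scale for relatedness refers to something given to one group. A control known to be a control can hardly be graded as having a device-related event, while a BMP child with the same wound infection can. Because the device is placed at surgery, the timing element of the *Possibly* grade is easily met by a perioperative event in the BMP group.

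Documenting safety is Specific Aim 2, and this composite is the only between-group comparison of adverse events that 6.1 and 6.2 specify. The adverse-event count comparison under Analyses in 6.2 is between the two BMP doses. The result would therefore depend partly on who attributed the events and what they knew.

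**Working it through.** The plan states no rate, test or power for this composite, so there is no figure to reproduce. The check has three parts.

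**1. What each group can contribute**

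| Component | Depends on attribution? | BMP group | Control group |
|---|---|---|---|
| Serious treatment-related event | Yes, on the 5.9 device scale if that scale is used | Can qualify | Can hardly qualify if treatment is known |
| Refracture | No | Counts | Counts |
| Need for reoperation | No | Counts | Counts |

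**2. Size when true serious-event rates are equal**

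Inputs:
- p0, the refracture or reoperation rate: 25% in both groups. This is an assumption, set at the refracture rate in 3.7 among 16 patients who healed after BMP-2.
- s, the true serious-event rate, equal in both groups: 5 to 30%, an assumption. The documents give no serious-event rate. The nearest figure is the 17% total complication rate under Early Stopping Rule in 6.2, which is not limited to serious events.
- r, the share of BMP serious events called related: 25 to 100%, an assumption.
- The matching share in controls: 0, an assumption.
- Serious events independent of refracture and reoperation, an assumption.

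Formulas: BMP failure = 1 − (1 − p0)(1 − s·r); control failure = p0; gap = (1 − p0)·s·r.

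| s | r | BMP | Control | Spurious gap |
|---|---|---|---|---|
| 5% | 25% | 25.9% | 25.0% | 0.9 points |
| 17% | 50% | 31.4% | 25.0% | 6.4 points |
| 17% | 100% | 37.8% | 25.0% | 12.8 points |
| 30% | 100% | 47.5% | 25.0% | 22.5 points |

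If every serious event counts in both groups, both rates at s = 17% are 1 − 0.75 × 0.83 = 37.8%, and the gap is 0.

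*Overlap.* Let v be the share of attributed serious events in children who have already failed by refracture or reoperation. Then gap = (1 − v)·s·r, and independence corresponds to v = p0 = 25%. At s = 17% and r = 100%, the gap is 17.0 points with v = 0, 12.8 with v = 25%, 8.5 with v = 50%, and 0 with v = 100%.

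*Chance of a false signal.* No test is named, so a two-sided Fisher exact test at 0.05 is assumed, with 26 BMP and 15 control patients (the minimum goal at the end of 6.2), s = 17% and p0 = 25%. The chance of p ≤ 0.05 is 4.7% at r = 50% and 9.6% at r = 100%, against 3.2% when all serious events count in both groups.

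**3. Direction when BMP truly raises serious events**

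Take the serious-event component alone, with assumed true rates of 30% in BMP and 10% in controls, a true gap of 20 points. With no control event attributed, the counted gap is 30% × r:
- r = 50%: 15 points, which understates harm by 5.
- r = 100%: 30 points, which overstates it by 10.
- Break-even: r = 1 − 10/30 = 0.67.

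So the sign of the error is not fixed. It depends on the true rates and on the share attributed.

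**The case against.** The strongest reply is that 6.1 says treatment-related, not device-related, and never refers to the scale in 5.9. The protocol describes both groups as treated, and the common operation sits under Treatment Program in section 5. The research monitor in 6.4 comments on relationship to study participation, which can apply to a control. On that reading a control's surgical-site infection could qualify. This stands as far as it goes: the defect is partly an undefined term. But no scale is written for the wider reading, the monitor's comment is not linked to the composite, and the grading that sites are told to do is against the device.

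A reader might infer that a control event can never be counted, or that the composite is biased against BMP in all cases. The documents support neither. A blinded non-surgeon site PI in the Randomized arm could attribute a control's event to the device. The direction against BMP needs similar true serious-event rates; part 3 of the working shows the reverse. Blinding still gives only partial protection, because 6.2 expects most data to come from the Choice Arm and the surgeon knows the treatment in both arms.

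Three further points stand. Two of the three components do not depend on attribution. Serious events overlap with reoperation, since an infection or ectopic bone that needs surgery already counts in either group. And Aim 2 is also served by all-cause event recording, antibody testing in all subjects and a separate toxicity stopping rule, although none of these is a planned between-group comparison of serious events.

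**Conclusion.** The concern holds in a limited form. The serious-event component of the safety composite rests on an undefined term, and the only scale available to apply it refers to a device that one group does not receive, often with the rater aware of treatment. That component is therefore not counted on the same rule in both groups.

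The range of about 1 to 22.5 points rests wholly on the assumed rates, on no attribution in controls and on independence. Overlap beyond chance, or any attribution of control events, would make it smaller. At the planned numbers this is a matter of a few children: 12.8 points of 26 is about 3.3. It is enough to colour the safety conclusion, but formal significance would remain unlikely in most of these settings. The primary RUST comparison is not touched.

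**What to change.** In 6.1, for the between-group comparison, define failure as any serious adverse event regardless of attribution, refracture, or need for reoperation, counted identically in both groups. Report device-related serious events separately and descriptively for the BMP group, and state which of the five grades count as related.

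The cost is a wording change, because 5.9 already requires all events to be recorded in both groups regardless of cause. The downside is that serious events unrelated to the surgery or the device add some noise to both groups and may dilute a real signal in a sample this small. The descriptive device-related listing partly offsets that.

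An alternative is to define treatment-related as related to the whole study procedure, surgery included, with adjudicators blinded to group. That limits the noise but needs an adjudication process that the plan does not have.

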6.2 Power Analysis/Sample Size Justification

The primary study endpoint will be the subject's RUST score 12 months after surgery. The radiology panel determining RUST score will be blinded to the treatment status of all patients, whether in the Choice or Randomized arms. The two treatment groups will be compared with

respect to the RUST score using the Wilcoxon Rank Sum Test at the one sided 0.05 significance level.

Data from the TSRH of 12 patients treated without BMP but an identical surgical protocol showed RUST scores at 12 mos post surgery of: Score 4-7 in 33%; Score of 8-9 in 42%; and score of 10-12 in 25%. If the use of BMP improves these scores to: 15% 4-7; 20% 8-9, and 65% 10-12, as suggested by our data from [name] 16 patients treated with BMP, then it follows that for two patients randomly chosen, one from each treatment group, the probability that the patient in the BMP group will have a better score than the patient in the Control group is .691. Using a standard formula [Kolassa, 1995] implemented in nQuery Advisor® 7.0 this study with the initially planned sample size of 50 (25 per group) will have 86% power for a Wilcoxon Rank Sum Test at the one sided p.05 significance level.

Study Modification: Based on data from the first year of the trial, more eligible patients declined to participate than agreed to participate; however, in many of these cases the family would have agreed to a Parental Preference trial. Similar Parental Preference clinical trials have achieved acceptance within the orthopedic field, as demonstrated by the large BrAIST study of bracing versus no bracing for adolescent scoliosis [Weinstein et al, 2013; Schwieger et al., 2016]. The study was thus modified after initiation to allow a **Choice Group**, wherein after offering whether a potential participant had a preference, this would be honored. If there were no preference or if there is no option to obtain BMP at the institution where the participant is being seen, they would be **randomized** to BMP or Control using a 2:3 randomization. The rationale for this unbalanced randomization is to obtain or achieve enough controls to have a reasonable comparison of the effect of BMP. It is expected by participating surgeons that more patients would prefer the BMP arm to the Control arm if given the choice.

We anticipate that this would leave the study with a potential slight imbalance in BMP treatment and controls. Thus, we evaluated the impact on the primary analysis given various scenarios on recruitment and testing treatment effects assuming the results of choice and randomized allocation could be pooled.

The study is limited by the company's allocation of just 26 BMP devices, so we examined the power of the study under various scenarios of BMP treated to Controls. The table below shows the power, along with the sample sizes (shown in italics in the table in the 4th and 5th rows), if the study ends up with 5 and 26 patients in Usual Care versus BMP, up to comparison of 20 Usual Care versus 26 BMP across the columns of the table. The power ranges from 46% power to detect a difference in RUST scores using a 1 tailed test at 0.05 to over 80% (as per our original primary analysis and endpoint). This is testing the RUST scores assuming UC of: 33% (Rust Scores 4-7), 42% (8-9) and 25% (10-12) compared to 15% (4-7); 20% (8-9) and 65% (10-12). So if we enroll at least 10 -15 controls, we have approaching 70% power to declare a significant difference. Obviously, we need to have a sufficient number of controls to enhance the power, and to help ensure this result, we will randomize 3 controls to 2 BMP cases in the randomization to enhance our ability to achieve at least 10 controls.

**Power using a Wilcoxon (Mann-Whitney) rank-sum test that $P(X < Y) = .5$ (ordered categories) (unequal n's), One sided Type I error=0.05
(Control Rust scores 33% (4-7), 42% (8-9), 25% (>=10) versus BMP 15%, 20%, 65% respectively)**

	1	2	3	4	5	6	7	8
Number of categories, k	3	3	3	3	3	3	3	3
$p_1 = P(X < Y)$	0.702	0.702	0.702	0.702	0.702	0.702	0.702	0.702
Power (%)	46	51	56	59	62	65	76	82

n_1	26	26	26	26	26	26	26	26
n_2	5	6	7	8	9	10	15	20

Our analysis will be a primary analysis combining the Choice and randomized participants. We will perform sensitivity analyses within the Choice and Randomized cohorts separately. Given the limited sample sizes, we do not expect significant differences, but will examine descriptive statistics comparing the Choice Group to the Randomized Group. We will examine the RUST scores amongst those who choose BMP versus those who refuse and choose usual care. We will of course, consider comparisons to historical controls should the results prove clearly different between the Choice and Randomized Groups.

As noted above we are likely giving up some power with this change to a Choice Design. Our assumption based on the current rate of declining to participate is that more patients will chose the BMP arm above the Control arm, but if we are incorrect, we would have adequate power (76% - 82%) if we were able to enroll 15-20 patients in the Control arm and 26 patients in the BMP arm. Even in a worse scenario that we were only able to recruit 10 patients to the Control arm + 26 to BMP, we would still have reasonable power of 65% to show a difference between the groups.

It is important to note that, although participants and providers in the Choice Arm will no longer be blinded to the treatment status of the participants, the Primary Outcome Measure (RUST score), will be determined by a group of 4 radiologists, all blinded to the treatment status of all participants.

Missing data: Reason for any missing 12 month radiographic data will be recorded by treatment group. Data from subjects missing the 12 month radiograph will not be included, unless multiple imputation is applied. Although minimal data are expected to be missing, multiple imputation technique will be used if 5% or more data are missing. This multiple imputation will replace the missing value with a set of plausible values that represent the uncertainty about the right value to impute. The multiply imputed data sets will then be analyzed by using the Wilcoxon Rank Sum Test for complete data on each and combining the results from these analyses. The variables used for the imputation will be RUST score at 6 months, age, prior surgery (Yes=1, No=0), and timed 10 meter walk at 12 months post-surgery.

Generalizability of the Results:

As we noted above, we expect that most of the data from this study will be generated by the choice arm and hope to maintain at least 10 randomized controls. We will compare the participant characteristics as well as Rust Scores between any controls identified by choice to those controls by randomization and more importantly RUST scores between the choice and randomized BMP treated arms. We will look at the overlap of the confidence intervals and test the equivalence of the two sets of results using two one sided tests of equivalence at the 5% level with an equivalence margin of 0.513. The margin of equivalence of 0.513 was derived based on the hypothesized difference between treatment and control originally planned and assuming these scores are normal continuous variables. Here we used the midpoint of each Rust Scoring Interval (5.5, 8.5 and 11) and computed the average Rust score for each group based on the hypothesized distribution in each group and ended up with a mean of 9.675 in the BMP group compared to 8.135 in the control group yielding an average difference in Rust Score of 1.54. We took 1/3 of the difference between the treatment average Rust score and the usual care Rust score ending up with an equivalence margin of 0.513. Since these sample sizes are small, we don't expect to reject the null hypothesis of differences as the power is probably low, but if they are different we understand that pooled results will be difficult to interpret. If these

tests of Choice versus Randomized treatment arms are not able to reject nonequivalence, we understand that this is not strong evidence for a lack of poolability between choice and randomization. Nevertheless, it will be sufficient to allow a comparison and calculation of the differences between the treatments and an overall assessment of the benefit of BMP in healing especially if we can demonstrate equivalence. Sensitivity analyses will be conducted using pooled and unpooled results as no statistical evidence of a lack of nonequivalence is not absolute evidence for nonequivalence.

Analyses:

All statistical analyses will be performed using SAS (version 9.3). All analyses are based on evaluable patients, as defined in section 10.5 with sensitivity analyses considering inevaluable patients as failures (scores 4-7). Summary statistics will be used to describe the study population (such as ranges, medians of ages, gender, baseline performance characteristics). The quality of life assessment in this study is based on the Pediatric Outcomes Data Collection Instrument, the PedsQL Pediatric Pain Questionnaire, and the 10 meter Timed Walk. From data collected on these questionnaires, scales are formed that measure domains such as global functioning, extremity and physical function, transfers and basic mobility, sports/physical function, happiness, and pain/comfort. These QOL and pain measures will be given pre-surgery, 3 months, 6 months, and 12 months after surgery. Since the scales are continuous, summary statistics will be generated for each measure at each time-point. The paired t-test will be used to look at changes in these measures from pre-treatment levels through 12 months. Longitudinal data analysis methods will be used to evaluate long-term changes in these measure using regression techniques employing mixed models.

In order to determine factors which may be prognostic for the success of BMP-2 treatment, we will perform Wilcoxon Rank Sum Tests to within each group to compare:

- 1) age \leq 8 years versus age $>$ 8 years
- 2) prior surgery versus no prior surgery; and
- 3) prior rhBMP-2 exposure versus rhBMP-2 naïve.

Regarding dose of rhBMP-2, those with 4.2 mg of rhBMP-2 implanted will be compared to those with 8.4 mg of rhBMP-2 implanted with respect to success rate using a chi square contingency table and with respect to number of adverse events using the Wilcoxon Rank Sum Test.

Relationships between quality of life measures and other variables (i.e., pain) will be investigated using correlational analyses. Performance status will be assessed using the Karnofsky Performance Scale. Generalized linear models will be used to evaluate changes in these scales and scores over time.

Early Stopping Rule

While BMP-2 has been evaluated extensively in non-NF1 patients, it has not been administered as a clinical trial in children with NF1 who have tibial pseudarthrosis. An early stopping rule will be invoked to prevent accrual of patients onto the study in the event that BMP-2 is associated with a higher than acceptable rate of severe toxicity identified at 6 weeks and 12 weeks post surgery [types: Grade 3 opportunistic infection, Grade 4 rash, Grade 3 hypertension, grade \geq 3 allergic reaction (determined by clinical assessment and antibody levels), grade 3 renal toxicity, severe ectopic bone formation requiring surgery, or the development of malignant peripheral nerve sheath tumor or other cancers]. Toxicity assessment will be graded according to the National Cancer Institute Common Terminology Criteria for Adverse Events (CTCAE) (v4.03). After 10 patients are enrolled in each arm, toxicity will be reviewed and if greater than the

number of patients shown in the table below experiences severe toxicity, accrual will be stopped. Based upon results calculated using the binomial distribution, the following holds true for the table as a whole:

True probability of toxicity	Chance of stopping early
.10	7%
.20	32%
.25	47%
.30	62%
.40	83%

Number of patients	Trial will be stopped if the number of patients with severe toxicity is greater than or equal to the number below
10	3

Should the number of patients showing severe toxicity during treatment with BMP-2 exceed 25% of the total number of patients enrolled, the study committee and medical monitor will review the toxicities and define whether a protocol revision is required. This 25% level was determined based on prior studies showing a total complication rate of 17% in pediatric patients treated with BMP-2 [[name] and [name], 2010].

Likewise, the trial may be stopped early if at least 6 patients of the first 10 enrollees in the BMP-2 arm have complete failure of union by 12 months postop (RUST score of 5 or less). This will be determined after the first 10 enrollees in the BMP-2 arm have completed the 12 month assessment. The entire study will be terminated if the BMP-2 group is stopped early due to toxicity or failure of union.

Since subjects, once they have had surgery, will need to be seen regularly for follow-up, we expect little or no attrition or loss to follow-up. Therefore, we will plan to enroll a total of between 36-52 patients, with a minimum goal of 15 eligible patients in the control arm and 26 patients in the BMP arm.

